Hematology				X	Unscheduled blood chemistry and hematology panels may be performed at the discretion of the investigator.
Serum chemistry				X	Unscheduled blood chemistry and hematology panels may be performed at the discretion of the investigator.
Fasting lipid profile				X	Patients should not eat or drink anything except water for 12 hours prior to sample collection. If a patient attends these visits in a nonfasting state, this will not be considered a protocol violation.
Urinalysis				X	
HBV PCR	X			X	Any enrolled subject who is HBcAb+ will undergo monitoring of HBV PCR. Any subject with a positive HBV PCR test at any time must be discontinued from the study and receive appropriate follow-up medical care, including consideration for antiviral therapy.
Immunogenicity		X		X	
Serum for LY3074828 concentration (PK)		X		X	
Urine pregnancy test				X	To be performed only on women of child bearing potential.
hsCRP	X	X	X	X	
Serum/ plasma for storage/ exploratory biomarkers	X	X	X	X	
CCI [REDACTED]				■	

Abbreviations: BP = blood pressure; C-SSRS = Columbia–Suicide Severity Rating Scale; DLQI = Dermatology Life Quality Index; DNA = deoxyribonucleic acid; ECG = electrocardiogram; ET = early termination; FSH = follicle stimulating hormone; HBcAb = anti-hepatitis B core antibody; HBsAb = hepatitis B surface antibody; HBsAg = hepatitis B surface antigen; HBV = hepatitis B virus; HCV = hepatitis C virus; Hep C = hepatitis C; HIV = human immunodeficiency virus; hsCRP = high-sensitivity C-reactive protein; mins = minutes; PASI = Psoriasis Area and Severity Index; PatGA = Patient’s Global Assessment; PCR = polymerase chain reaction; PK = pharmacokinetic; PPD = purified protein derivative; PRN = as needed; PSS = Psoriasis Symptom Scale; PSSI = Psoriasis Scalp Severity Index; Q8W = every 8 weeks; RNA = ribonucleic acid; SF-36 = Medical Outcomes Study 36-Item Short Form Health Survey; sPGA = static Physician’s Global Assessment; TB = tuberculosis; V = visit.

- a A subject who chooses to enter the separate long-term extension study but is not able (for example, due to unresolved safety concerns) will continue to be evaluated at the follow-up period visits in Study AMAF until the subject is determined to be eligible for the separate long-term extension study, at which time the assessments for V804/ET will be performed.

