**Treatment Arms and Duration:**

The study will include 4 arms: 3 experimental arms in which LY3074828 will be dosed SC at 30 mg, 100 mg, or 300 mg and 1 placebo comparator arm. During the double-blind, 16-week induction period, study drug will be administered at Week 0 and Week 8. At the end of the induction period (Week 16), subjects will continue treatment in the maintenance period which is intended to explore 1 of 2 treatment strategies through Week 104. Dose levels in the maintenance period will remain double-blind; however, dosing strategy will be open-label. The maintenance period consists of 88 weeks of treatment. All placebo subjects and subjects assigned to treatment with LY3074828 who have a <90% improvement in Psoriasis Area and Severity Index (PASI) from baseline (PASI 90) at Week 16 will receive LY3074828 300 mg SC every 8 weeks (Q8W) during the entire maintenance treatment period. Subjects with  $\geq$ PASI 90 (as needed [PRN] dosing group) at Week 16 will only be dosed with LY3074828 at the baseline dose level assignment no more frequently than Q8W when disease activity level is <PASI 90, and this will continue until  $\geq$ PASI 90 is regained. The maintenance period will be followed by a 16-week follow-up period to assess subject safety and study drug efficacy. Subjects who complete the maintenance period may be eligible to participate in separate long-term extension study.

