PPD/QuantIFERON-TB Gold (per local guidelines)	X							Subjects will return 2 to 3 days after Visit 1 to have their PPD test read.
ECGs	X						X	This should be completed prior to any study dose administration or blood draw. Subjects should be supine for approximately 5 to 10 minutes before ECG collection and remain supine but awake during ECG collection.
C-SSRS	X	X	X	X	X	X	X	
CCI [REDACTED]		■	■	■	■	■	■	[REDACTED]
Study drug dosed		X			X		X	At Week 16, subjects will only receive study drug dosing if PASI <90.

Induction Dosing Period (Visits 1-7)								
Visit No.	V1	V2	V3	V4	V5	V6	V7	Comments
Week Relative to Study Drug Start	-4	0	2	4	8	12	16	All activities should be completed prior to any study dose administration unless otherwise stated below.
Day with Visit Tolerance Interval	≤28 from V2	0	14 ± 2	28 ± 3	56 ± 5	84 ± 5	112 ± 5	Visit 1 procedures may be conducted over more than 1 day as long as all tasks are completed within the allowable visit tolerance (at least 3 days should be allowed for receipt of laboratory test results).
Clinical Efficacy								
PASI	X	X	X	X	X	X	X	
sPGA	X	X	X	X	X	X	X	
PSSI, if applicable		X	X	X	X	X	X	Once a subject experiences symptoms related to scalp involvement, this form should be completed at all remaining indicated visits.
Whole body photographs		X					X	If subject has agreed to whole body photographs.
Health Outcomes								
PSS	Electronic Diary Taken Daily from Screening (V1) up to Week 16 (V7)						X	
PatGA		X	X	X	X	X	X	
DLQI		X	X	X	X	X	X	
SF-36		X					X	
Laboratory Tests								
Hematology	X	X	X	X	X	X	X	Unscheduled blood chemistry and hematology panels may be performed at the discretion of the investigator.
Lymphocyte subsets		X					X	
Serum chemistry	X	X	X	X	X	X	X	Unscheduled blood chemistry and hematology panels may be performed at the discretion of the investigator.
Urinalysis	X	X			X		X	

Induction Dosing Period (Visits 1-7)								
Visit No.	V1	V2	V3	V4	V5	V6	V7	Comments
Week Relative to Study Drug Start	-4	0	2	4	8	12	16	All activities should be completed prior to any study dose administration unless otherwise stated below.
Day with Visit Tolerance Interval	≤28 from V2	0	14 ± 2	28 ± 3	56 ± 5	84 ± 5	112 ± 5	Visit 1 procedures may be conducted over more than 1 day as long as all tasks are completed within the allowable visit tolerance (at least 3 days should be allowed for receipt of laboratory test results).
HBsAg, HBcAb, HBsAb	X							

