Vital signs (BP and heart rate), body temperature only if clinically indicated	X	X	X	X	X	X	X	X	X	X	X	Sitting blood pressure and pulse, to be obtained at approximately the same time as ECG measurements or blood sampling. When multiple assessments are scheduled for the same time point, the order of completion should be as follows: ECG, vital signs, and then blood sampling.
ECGs									X			ECGs should be performed before any blood is drawn. Subjects should be supine for approximately 5 to 10 minutes before ECG collection and remain supine but awake during ECG collection.
C-SSRS	X	X	X	X	X	X	X	X	X	X	X	
CCI												

Maintenance Dosing Period (Visits 8-18)												
Visit No.	V8	V9	V10	V11	V12	V13	V14	V15	V16	V17	V18	Comments
Week Relative to Study Drug Start	20	24	28	32	36	40	44	48	52	56	60	All activities should be completed prior to any study dose administration unless otherwise stated below.
Day with Visit Tolerance Interval	140 ± 5	168 ± 5	196 ± 5	224 ± 5	252 ± 5	280 ± 5	308 ± 5	336 ± 5	364 ± 5	392 ± 5	420 ± 5	
Study drug dosed	X	X	X	X	X	X	X	X	X	X	X	Subjects assigned to PRN will be evaluated at every visit to determine if dose needed. Subjects assigned to Q8W will get dosed on odd number visits.
Clinical Efficacy												
PASI	X	X	X	X	X	X	X	X	X	X	X	
sPGA	X	X	X	X	X	X	X	X	X	X	X	
PSSI, if applicable	X	X	X	X	X	X	X	X	X	X	X	Once a subject experiences symptoms related to scalp involvement, this form should be completed at all remaining indicated visits.
Whole body photographs				X					X			If subject has agreed to whole body photographs.
Health Outcomes												
PSS				X					X			
PatGA				X					X			
DLQI				X					X			In addition to the marked visits, DLQI also taken at PRN dosing or rescue treatment visits.
SF-36				X					X			
Laboratory Tests												
Hematology	X	X	X	X	X	X	X	X	X			Unscheduled blood chemistry and hematology panels may be performed at the discretion of the investigator.
Lymphocyte subsets									X			

Maintenance Dosing Period (Visits 8-18)												
Visit No.	V8	V9	V10	V11	V12	V13	V14	V15	V16	V17	V18	Comments
Week Relative to Study Drug Start	20	24	28	32	36	40	44	48	52	56	60	All activities should be completed prior to any study dose administration unless otherwise stated below.
Day with Visit Tolerance Interval	140 ± 5	168 ± 5	196 ± 5	224 ± 5	252 ± 5	280 ± 5	308 ± 5	336 ± 5	364 ± 5	392 ± 5	420 ± 5	

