## 5. Study Design

### 5.1. Overall Design

Study AMAF is a multicenter, randomized, parallel-arm, placebo-controlled trial with 4 study periods in subjects with moderate-to-severe plaque psoriasis.

[figure not shown]
**Screening Period (≤4 weeks):** Subjects will be evaluated for study eligibility ≤28 days before the baseline visit (Visit 2/Week 0). At the baseline visit (Visit 2), subjects who fulfill the eligibility criteria will be randomized to 1 of 4 induction treatment arms.

**Induction Period (16 weeks):** A double-blind, 16-week induction period is designed to establish the efficacy and safety of LY3074828 administered at Visit 2 (Week 0) and Visit 5 (Week 8). Subjects will be randomized to 1 of 4 induction treatment arms (LY3074828 30 mg SC, LY3074828 100 mg SC, LY3074828 300 mg SC, and placebo every 8 weeks [Q8W]) stratified on the basis of previous exposure to biologic therapy for treatment of psoriasis.

**Maintenance Period (88 weeks):** The maintenance period consists of 88 weeks of treatment. At the end of the induction period (Week 16), subjects will continue treatment in the maintenance period which is intended to explore 1 of 2 treatment strategies through Week 104. All placebo subjects and subjects assigned to treatment with LY3074828 who have a <90% improvement in Psoriasis Area and Severity Index (PASI) from baseline (PASI 90) at Week 16 will receive LY3074828 300 mg SC Q8W during the entire maintenance period. Subjects with ≥PASI 90 (as needed [PRN] dosing group) at Week 16 will only be dosed with LY3074828 at the baseline dose level assignment no more frequently than Q8W when disease activity level is <PASI 90, and this will continue until ≥PASI 90 is regained. See Section 7.8.2 for maintenance period rescue treatment.

Subjects who complete Week 104 (Visit 29) of Study AMAF may be eligible to receive additional LY3074828 treatment by choosing to enroll in a separate long-term extension study, pending competent authority and/or ethical review board (ERB) approvals to conduct the separate long-term extension study.

**Follow-up Period (16 weeks):** Subjects who do not enroll in the separate long-term extension study will complete the follow-up period of Study AMAF. The follow-up period will include a visit every 4 weeks for a total of 16 weeks following Visit 29 to assess subject safety and study drug efficacy. [Figure AMAF.1](#) illustrates the study design.

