### 5.4. Scientific Rationale for Study Design

This study will examine the effect of 16 weeks of induction dosing followed by evaluation of continuous dosing compared with PRN dosing in the maintenance period. All placebo subjects and subjects assigned to treatment with LY3074828 that have a <PASI 90 at Week 16 will receive LY3074828 300 mg SC Q8W during the entire maintenance treatment period. Subjects

with  $\geq$ PASI 90 (PRN dosing group) at Week 16 will only be dosed with LY3074828 at the baseline dose level assignment no more frequently than Q8W when disease activity level is  $<$ PASI 90, and this will continue until  $\geq$ PASI 90 is regained. The 2-year study duration will allow evaluation of the frequency of dosing a subject needs to maintain a high level PASI response.

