**Table AMAF.3. Treatment Regimens**

Treatment Group	Description
Induction Period	
LY Dose Arm 1	30 mg LY given SC Q8W
LY Dose Arm 2	100 mg LY given SC Q8W
LY Dose Arm 3	300 mg LY given SC Q8W
Comparator	Placebo given SC Q8W
Maintenance Period	
LY Dose Arm 1	If <PASI 90 at Week 16: 300 mg LY given SC Q8W If ≥PASI 90 at Week 16: 30 mg LY given SC PRN
LY Dose Arm 2	If <PASI 90 at Week 16: 300 mg LY given SC Q8W If ≥PASI 90 at Week 16: 100 mg LY given SC PRN
LY Dose Arm 3	If <PASI 90 at Week 16: 300 mg LY given SC Q8W If ≥PASI 90 at Week 16: 300 mg LY given SC PRN
Placebo	300 mg LY given SC Q8W

Abbreviations: LY = LY3074828; PASI = Psoriasis Area and Severity Index; PASI 90 = 90% improvement in PASI from baseline; PRN = as needed; Q8W = every 8 weeks; SC = subcutaneous.

SC administration of LY3074828 will be given in up to 4 injections (maximum volume 1.5 mL per injection). All subjects should be monitored after dosing according to investigator practice or local standard of care. Detailed instructions for investigational product administration will be provided separately by the sponsor.

Investigational product will be prepared at the site by unblinded pharmacists or other trained personnel. Investigational product will be administered at the site by blinded nurses or other trained personnel.

The investigator or his/her designee is responsible for the following:

- explaining the correct use of the investigational agent(s) to the site personnel
- verifying that instructions are followed properly
- maintaining accurate records of investigational product dispensing
- at the end of the study returning all unused medication to Lilly, or its designee, unless the sponsor and sites have agreed all unused medication is to be destroyed by the site, as allowed by local law

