### 10.3.1.2. General Considerations for Analyses in the Maintenance Period

For maintenance period efficacy analysis, unless otherwise stated, baseline is defined as the last available value before the initial randomization in the induction period which in most cases will be the value recorded at Week 0 (Visit 2).

For maintenance period safety analysis, for subjects

- randomized to placebo in the induction period and for subjects who did not achieve PASI 90, baseline is defined as the last available value before the treatment reassignment in the maintenance period (Week 16, Visit 7)
- who did achieve PASI 90, baseline is defined as the last available value before the initial randomization which in most cases will be the measure recorded at Week 0 (Visit 2)

Change from baseline and 95% confidence interval will be calculated by treatment as the visit value of interest minus the baseline value for continuous variables. The proportion and 95% confidence interval will be reported by treatment for categorical variables.

The Kaplan-Meier product limit method will be used to estimate the survival curves for time-to-event variables; median time to loss of response will be summarized by treatment.

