6.1.1. Subject Populations for Analyses

For purposes of analysis, populations for analyses are described in [Table 6.1](#).

Table 6.1. Subject Populations for Analyses

Population	Description
Intent-to-treat (ITT) (Induction Period Efficacy)	All randomized subjects, even if the subject does not take the assigned treatment, does not receive the correct treatment, or otherwise does not follow the protocol: 
 Unless otherwise noted, efficacy and health outcomes analyses for the Induction Period will be conducted on this population. Subjects will be analyzed according to the treatment to which they were assigned.
Induction Period Safety	All randomized subjects who received at least 1 dose of study treatment: 
 Unless otherwise noted, safety analyses for the Induction Period will be conducted on this population. Subjects will be analyzed according to the treatment to which they were assigned.
Maintenance Period Efficacy	All randomized subjects who have entered the Maintenance Period (see definition of entering Maintenance Period in Section 6.1.2.1): 
 Unless otherwise noted, efficacy, and health outcomes for the Maintenance Period will be conducted on this population. Subjects will be analyzed according to the treatment to which they were assigned in Maintenance Period.

Population	Description
Maintenance Period Safety	
All randomized subjects received at least 1 dose of study treatment who have entered the Maintenance Period (see definition of entering Maintenance Period in Section 6.1.2.1):
 
 • Unless otherwise noted, safety analyses for the Maintenance Period will be conducted on this population. • Subjects will be analyzed according to the treatment to which they were assigned in Maintenance Period, with all LY3074828 300 mg Q8W arms combined, that is, there will be 4 treatment groups in the Maintenance Period: 
 ○ LY 300 mg PRN ○ LY 100 mg PRN ○ LY 30 mg PRN ○ LY 300 mg Q8W (including subjects from 4 Induction Period treatment groups)

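### The Week 16 dosing comment in the Schedule of Activities has no placebo exception, so it conflicts with the assignment of every placebo subject to 300 mg Q8W in maintenance

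*Protocol*

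**What the plan says.** In the protocol's Schedule of Activities, the row for study drug dosing is marked at Visit 7 (Week 16), with the comment "At Week 16, subjects will only receive study drug dosing if PASI <90". The comment names no arm. For later visits the same row says "Subjects assigned to Q8W will get dosed on odd number visits".

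The regimen tables say something different for placebo. In Protocol Table AMAF.3 each LY3074828 arm is split by Week 16 PASI 90 status. The placebo row for maintenance carries no condition: "300 mg LY given SC Q8W". SAP Table 5.1 has the same structure. The design text in Protocol Sections 1, 5.1 and 5.4 and SAP Section 5.1 agrees: placebo subjects, and LY3074828 subjects below PASI 90, get 300 mg Q8W throughout maintenance.

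The analysis sections follow the tables. For the maintenance safety baseline, Protocol Section 10.3.1.2 groups subjects "randomized to placebo in the induction period and for subjects who did not achieve PASI 90", so placebo subjects are named separately from those who missed PASI 90. SAP Table 6.1 has three as-needed (PRN) groups, one per LY3074828 dose, and a single group "LY 300 mg Q8W (including subjects from 4 Induction Period treatment groups").

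**The concern.** A placebo subject at or above PASI 90 at Week 16 falls under two incompatible instructions. The treatment tables say to give 300 mg, and the Visit 7 comment says to give nothing. Staff who administer product are blinded (Protocol Section 7.1), so they cannot see that a responder is on placebo and cannot settle the conflict themselves. A rule based on PASI alone is one they could apply.

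At stake is the start of active treatment for a few placebo subjects, and a short undosed interval attributed to 300 mg Q8W. SAP Section 6.12.1.1 measures maintenance exposure from the last induction visit, so that interval would count there. The combined-period exposure starts at the first LY3074828 injection, so it would not count in that summary. Adverse events in the interval would be tabulated under 300 mg Q8W before any active dose.

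**Working it through.** **The plan's own figure.** SAP Section 5.2 assumes PASI 90 rates of 60% and 3%, 50 subjects per arm and a two-sided Fisher's exact test at 0.05, and states power above 99%. Exact enumeration over Binomial(50, 0.60) and Binomial(50, 0.03) gives 0.9999999, so the figure is reproduced. The Visit 7 dose cannot change it, because the Schedule requires that visit's assessments before any dose.

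**Is Week 16 a Q8W dosing visit?**
- The maintenance period starts on the date of the Week 16 PASI measurement (SAP Section 6.1.2.1).
- Visit 7 is marked for dosing, and the previous dose is at Visit 5 (Week 8).
- Later Q8W doses fall on odd-numbered visits.

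The first maintenance Q8W dose is therefore due at Visit 7.

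**The rules side by side at Week 16.**

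| Subject | Tables AMAF.3 and 5.1 | Visit 7 comment |
|---|---|---|
| LY3074828, below PASI 90 | 300 mg Q8W | Dose |
| LY3074828, PASI 90 or better | PRN, no dose yet | No dose |
| Placebo, below PASI 90 | 300 mg Q8W | Dose |
| Placebo, PASI 90 or better | 300 mg Q8W | No dose (conflict) |

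**How many subjects.** With n = 50 placebo subjects and response rate p, the expected number is n × p, and the chance of at least one is 1 − (1 − p)^50.
- SAP rate, p = 0.03: 50 × 0.03 = 1.5; 1 − 0.97^50 = 0.782.
- Assumed low, p = 0.01: 0.5; 1 − 0.99^50 = 0.395.
- Assumed high, p = 0.05: 2.5; 1 − 0.95^50 = 0.923.

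**Delay if the dose is withheld.** The next odd visit is Visit 9 (Week 24).
- Nominal: 168 − 112 = 56 days.
- Within the ±5-day windows: (168 − 5) − (112 + 5) = 46 days, to (168 + 5) − (112 − 5) = 66 days.

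**Doses lost.** Odd visits from 7 to 29 number 12; from 9 to 29, 11. For a subject who enters the extension, where that study's protocol decides the Visit 29 dose, the counts are 11 and 10. Either way, one Q8W dose is lost.

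**The case against.** The strongest reply is that the regimen is not in doubt. The design text, both treatment tables and the analysis populations all put placebo subjects on 300 mg Q8W, and one short schedule remark is the outlier. That is right about intent, and it is why the point is small. It does not remove the conflict, because the Schedule is an operative instruction at the visit.

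A second reply is that, taken literally, the comment refers to an absolute PASI score. The scale runs from 0 to 72, so every subject would qualify and nobody would be held. That reading does not rescue the comment. It would also dose LY3074828 responders, whom Table AMAF.3 assigns to PRN.

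A third is that the consequence is hypothetical. This stands in part. IWRS handles treatment assignment (Protocol Section 7.2), SAP Section 6.7 refers to its dispensing data, and unblinded staff prepare the product. These make an unnoticed omission less likely, though the available text does not say how a placebo responder is allocated at Week 16. The Week 24 start is also an inference: the odd-visit rule is written for Visits 8 to 29 and assumes the subject is then handled as Q8W.

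A reader might also infer that the PRN sentences in Protocol Sections 1, 5.1 and 5.4 and SAP Section 5.1 have the same gap, since responders "at Week 16 will only be dosed with LY3074828 at the baseline dose level assignment" and a placebo subject's baseline assignment is placebo. The documents do not support that. The sentence speaks of an LY3074828 dose level, which a placebo subject does not have. In each place it directly follows the sentence that assigns placebo subjects to 300 mg Q8W.

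**Conclusion.** The Visit 7 comment is wrong as written for one type of subject: a placebo subject at or above PASI 90 at Week 16. At the SAP's 3% rate this is about 1.5 of 50 subjects, with a 78% chance of at least one. Over assumed rates of 1% to 5% it is 0.5 to 2.5 subjects, with a chance of 39% to 92%. Each subject handled by the comment would start LY3074828 about 56 days late, with one fewer Q8W dose, while counted in the 300 mg Q8W group from Week 16. The counts assume 50 placebo subjects reaching Week 16 with a PASI assessment.

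It would go too far to conclude that doses were missed or that the efficacy results are affected. The documents show no missed dose. The primary endpoint is assessed before the dose in question, power is unchanged, and neither the induction comparisons nor any other planned comparison depends on it. This is a minor correction worth making because it is cheap.

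**What to change.** Replace the Visit 7 comment with: *At Week 16, all placebo subjects regardless of PASI response, and LY3074828 subjects with <PASI 90, receive LY3074828 300 mg; LY3074828 subjects with ≥PASI 90 (PRN group) are not dosed.* Issue the dose decision through IWRS, so that blinded site staff do not have to apply an arm-specific rule. The PRN sentences need no change. If all Week 16 visits are already past, check the dispensing records for placebo responders and document the intended rule.

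The cost is one schedule comment, with no change to the analysis or sample size. There is one small downside. Dosing strategy is open label in maintenance while the induction assignment stays blinded (Protocol Section 7.3), so a PASI 90 responder placed on Q8W can be inferred to have been on placebo. Using IWRS does not prevent that inference. It already follows from the treatment tables, and the rewording does not create it.

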### **9.1.4. Health Outcomes Assessments**

The following patient-reported questionnaires will be administered according to the Schedule of Activities (Section 2) in countries where the questionnaires have been translated into the native language of the region and linguistically validated. They should be completed before administration of study drug; before the subject's clinical examination; before the subject receives any tests or results; and before the subject's health, health data, or emotions are discussed.

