5.1. Summary of Study Design

Study AMAF is a multicenter, randomized, parallel-arm, placebo-controlled trial with 4 study periods in subjects with moderate-to-severe plaque psoriasis.

[figure not shown]
Screening Period (≤4 weeks): Subjects will be evaluated for study eligibility ≤28 days before the baseline visit (Visit 2/Week 0). At the baseline visit (Visit 2), subjects who fulfill the eligibility criteria will be randomized to 1 of 4 induction treatment arms.

Induction Period (16 weeks): A double-blind, 16-week Induction Period is designed to establish the efficacy and safety of LY3074828 administered at Visit 2 (Week 0) and Visit 5 (Week 8). Subjects will be randomized to 1 of 4 induction treatment arms (LY3074828 30 mg SC, LY3074828 100 mg SC, LY3074828 300 mg SC, and placebo every 8 weeks [Q8W]) stratified on the basis of previous exposure to biologic therapy for treatment of psoriasis.

Maintenance Period (88 weeks): The Maintenance Period consists of 88 weeks of treatment. At the end of the Induction Period (Week 16), subjects will continue treatment in the Maintenance Period which is intended to explore 1 of 2 treatment strategies through Week 104. All placebo subjects and subjects assigned to treatment with LY3074828 who have a <90% improvement in Psoriasis Area and Severity Index (PASI) from baseline (PASI 90) at Week 16 will receive LY3074828 300 mg SC Q8W during the entire Maintenance Period. Subjects with ≥PASI 90 PRN dosing group) at Week 16 will only be dosed with LY3074828 at the baseline dose level assignment no more frequently than Q8W when disease activity level is <PASI 90, and this will continue until ≥PASI 90 is regained.

Follow-up Period (16 weeks): The Follow-up Period will include a visit every 4 weeks for a total of 16 weeks following Visit 29 to assess subject safety and study drug efficacy.

[Figure 5.1](#) illustrates the study design.

^a Visits will occur every 4 weeks in the Maintenance and Follow-up Periods.
 Abbreviations: PASI = Psoriasis Area and Severity Index; PRN = as needed; Q8W = every 8 weeks.

Figure 5.1. Illustration of study design for Clinical Protocol I6T-MC-AMAF.

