6.3. Handling of Dropouts or Missing Data

6.3.1. Non-Responder Imputation (NRI)

Analysis of categorical efficacy and health outcome variables will be assessed using a NRI method. Subjects will be considered a non-responder for the NRI analysis if they do not meet the clinical response criteria or have missing clinical response data at the analysis time point. Randomized subjects without at least 1 postbaseline observation will also be defined as non-responders for the NRI analysis.

Due to the design, PRN subjects who got rescued will get a different treatment (300 mg LY SC Q8W), therefore the subsequent visits following the first dose of rescue treatment will be defined as non-responders in the analysis for the Maintenance Period.

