	Time to first loss of response (PASI 90, PASI 100) for PRN subjects	KM product limit curve; time to loss of response	Maintenance Period Efficacy Population	Maintenance Period

Measure	Variable	Analysis Method (Sections 6.1.3)	Population (Section 6.1.1)	Time Point
	Time to recapture of response (PASI 90, PASI 100) after first loss of response for PRN subjects	KM product limit curve; time to response recapture after first loss of response	Maintenance Period Efficacy Population	Maintenance Period
	Time to recapture of response (PASI 50, PASI 90) after loss of response for rescued subjects	KM product limit curve; time to response recapture after first loss of response	Rescue Period Efficacy Population	Rescue Period
sPGA	sPGA (0,1); sPGA (0)	Logistic regression analysis with NRI	ITT Population	All pairwise comparisons against placebo at all postbaseline visits in Induction Period
		Summary statistics with NRI	Maintenance Period Efficacy Population	All visits in Maintenance Period
		Summary statistics (As observed) or individual trajectory line plot if total number of subjects is too small	Rescue Period Efficacy Population	All visits in Rescue Period
BSA	BSA change from baseline	MMRM; mBOCF ANCOVA	ITT Population	All pairwise comparisons against placebo at all postbaseline visits in Induction Period
		MMRM	Maintenance Period Efficacy Population	All visits in Maintenance Period
PSSI	PSSI percent improvement from baseline (for subjects with scalp psoriasis involvement only); PSSI score (for all subjects)	MMRM; mBOCF ANCOVA	ITT Population	All pairwise comparisons against placebo at all postbaseline visits in Induction Period
		MMRM	Maintenance Period Efficacy Population	All visits in Maintenance Period
	PSSI score = 0 (for all subjects)	Logistic regression analysis with NRI	ITT Population	All pairwise comparisons against placebo at all postbaseline visits in Induction Period
	Summary statistics with NRI	Maintenance Period Efficacy Population	All visits in Maintenance Period	

Measure	Variable	Analysis Method (Sections 6.1.3)	Population (Section 6.1.1)	Time Point
DLQI	DLQI (0,1), DLQI (0)	Logistic regression analysis with NRI	ITT Population	All pairwise comparisons against placebo at all postbaseline visits in Induction Period
		Summary statistics with NRI	Maintenance Period Efficacy Population	All visits in Maintenance Period

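### SAP Table 6.3 analyses Maintenance DLQI at every visit, but outside Weeks 32, 52 and 104 forms are planned only for PRN subjects being dosed or rescued, so those rows would be artefacts

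*Protocol*

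**What the plan says.** - **Collection.** In the protocol's Schedule of Activities for Visits 8 to 18, the DLQI row is marked at Weeks 32 and 52, with the comment "In addition to the marked visits, DLQI also taken at PRN dosing or rescue treatment visits". The table for Visits 19 to 29 has one mark, displaced by a column in the available text. I read it as Week 104, which fits the secondary endpoint. No trigger comment is visible in that second table.
- **Trigger.** Protocol 5.1 doses PRN subjects "no more frequently than Q8W when disease activity level is <PASI 90".
- **Visit frequency.** SAP 5.1: "Visits will occur every 4 weeks in the Maintenance and Follow-up Periods".
- **Analysis.** SAP Table 6.3 gives, for DLQI (0,1) and DLQI (0) in the Maintenance Period Efficacy Population, "Summary statistics with NRI" at "All visits in Maintenance Period". DLQI total and domain change scores get ANCOVA at the same time points.
- **Imputation.** SAP 6.3.1 counts as non-responders those who "have missing clinical response data at the analysis time point", with no exception for visits where no form was due. For rescued PRN subjects, "the subsequent visits following the first dose of rescue treatment will be defined as non-responders in the analysis for the Maintenance Period".
- **Off-schedule data.** The one rule (SAP 6.1.3) concerns early-discontinuation visits. It removes such records from MMRM and keeps them for other analyses, including categorical ones.

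**The concern.** At an unmarked visit up to Week 60, whether a PRN subject has a DLQI form depends on the outcome: the form exists because response has fallen below PASI 90. A subject still at PASI 90 or better has no form, and neither does a subject on 300 mg Q8W. Non-responder imputation then turns the absence of a form into a failure, and a complete-case change score keeps only the relapsed.

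SAP 5.2 says the PRN results will inform Phase 3 maintenance dosing and points to Weeks 20 to 28. All three visits in that window are unmarked for DLQI. The documents do not say that DLQI will drive that decision, but these rows would be among the tables available when it is made.

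**Working it through.** **The plan's own figure.** The documents give no figure for DLQI in Maintenance. The only design figure, power over 99% in SAP 5.2 (60% against 3%, 50 per arm, two-sided Fisher's exact test at 0.05), reproduces as 0.9999999 by full enumeration. Nothing below depends on it.

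**1. Visits affected.** Weeks 20 to 104 every 4 weeks give (104 − 20)/4 + 1 = 22 visits. Three are marked, so 22 − 3 = 19 are unmarked:
- Weeks 20, 24, 28, 36, 40, 44, 48, 56 and 60: nine visits with triggered collection.
- Weeks 64 to 100 except none marked, that is every 4 weeks: (100 − 64)/4 + 1 = 10 visits with no visible trigger comment.

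**2. Responder rate under the literal rule.** Let f be the fraction of a group with a triggered form at the visit, and r the DLQI (0,1) rate among those subjects. Everyone else is imputed as a non-responder, so

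reported rate = f × r ≤ f.

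The true rate in the group does not enter.

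- *300 mg Q8W:* f = 0, so the rate is 0% apart from early-termination records. Table 5.1 of the SAP sends all placebo subjects and all active-arm subjects below PASI 90 to this group. With 60% response in every active arm and no dropout, that is 50 + 150 × 0.40 = 110 of 200 subjects.
- *PRN arms:* doses are at least 8 weeks apart and visits 4 weeks apart, so a subject can have a PRN dose at no more than one of two consecutive visits. The dosed fraction therefore averages at most 50% over such a pair, and the reported rate at most half of r if r is the same at both. Beyond that bound the size rests on assumed values:

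| f (assumed) | r = 20% (assumed) | r = 40% (assumed) |
|---|---|---|
| 5% | 1% | 2% |
| 10% | 2% | 4% |
| 25% | 5% | 10% |

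If the true rate were 50% to 80% (also assumed), the curve would sit at 1% to 10% at Weeks 20 to 28 and jump at Week 32, when all subjects are due a form.

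- *Weeks 64 to 100:* if no forms are triggered there, the literal rule gives about 0% in every group.

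**3. Change from baseline.** At the nine triggered visits the ANCOVA contains relapsed PRN subjects and, early-termination records aside, nobody on Q8W. SAP 5.2 projects 9, 18 and 22 PRN subjects (30, 100 and 300 mg) past Week 20 at the primary data lock. With f = 10% that is 0.9, 1.8 and 2.2 forms; with f = 25%, 2.25, 4.5 and 5.5.

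**4. Does an existing rule remove these records?** The off-schedule rule in SAP 6.1.3 misses them twice: it covers early-discontinuation visits, whereas these are triggered dosing visits, and it acts only on MMRM, whereas Maintenance DLQI uses ANCOVA and imputed proportions. The rescue rule in SAP 6.3.1 settles visits after the first rescue dose but not PRN dosing visits.

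**The case against.** **The time-point wording is stock text.** Table 6.3 uses the same phrase for SF-36, PatGA and PSS, which have no triggered collection. Its Induction rows ask for SF-36 at all postbaseline visits although SF-36 is collected at one. The authors probably meant visits at which the measure is collected, and the choice of ANCOVA over MMRM suggests that they knew DLQI was sparse. This stands, and for Weeks 64 to 100 it may dispose of the problem. It does not do so for the nine visits from Week 20 to 60, because triggered forms make those visits collected ones for a relapse-selected subset. Treating a form that was never due as not missing does not help either: the denominator shrinks to the relapsed, and the table shows r in place of f × r.

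**The artefact would be visible.** SAP 6.1 has categorical tables show how many patients provided data. A careful reader would notice, but the displayed rate would remain wrong.

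**Stronger readings that the documents do not support:**
- *That PRN dosing is made to look worse than Q8W.* Under the literal rule Q8W shows about 0% at the same visits, so PRN could look better.
- *That a protocol DLQI endpoint is compromised.* The secondary endpoint is mean change at Weeks 52, 104 and 120, all scheduled. Maintenance responder rates are descriptive.
- *That every triggered form is selected by current response.* Once rescue starts it continues whatever the PASI, and SAP 6.1.2.1 places those visits in a separate Rescue Period.
- *That triggered forms necessarily break the questionnaire order.* Protocol 9.1.4 asks for completion before the "clinical examination; before the subject receives any tests or results", and PASI decides whether a PRN dose is due. Sites could still give the DLQI to PRN subjects on arrival, and nothing says that subjects learn of their relapse first. The conflict is an inference.

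**Conclusion.** The point holds as a gap in the SAP. For nine Maintenance visits (Weeks 20 to 60 apart from 32 and 52), Table 6.3 requests DLQI results that depend on who was measured, and no rule sets the triggered forms aside.

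The result for Q8W, about 0% apart from early-termination records, follows from the literal rule alone. So does the ceiling in a PRN arm: the fraction dosed at the visit, again apart from early-termination records. The 1% to 10% range is illustrative and rests on assumed dosing and response rates. The Week 104 mark is my reading of a displaced column. Whether the artefact reaches the output depends on how the table is programmed.

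Both strategies are affected, with no fixed direction between them. The primary endpoint and the secondary DLQI endpoint are untouched. The correction is worth making because the written rule can give a wrong table and costs almost nothing to repair.

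**What to change.** - In Table 6.3, limit the Maintenance DLQI rows (responders with imputation, and change from baseline) to the visits scheduled for all subjects: Weeks 32, 52 and 104.
- Report DLQI from PRN dosing visits in a separate table, as observed, with the number assessed, labelled as collected at loss of response.
- Put DLQI from rescue visits in the as-observed Rescue Period summary. Table 6.3 has no DLQI row for that period, so add one, and state where the form from the first rescue visit goes, since SAP 6.1.2.1 ends Maintenance and starts Rescue on the same date.
- Optionally, reconcile the timing of triggered forms with Protocol 9.1.4, and state whether the trigger applies after Week 60.

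The analysis changes are SAP wording and one added row. They need no new data. The cost is fewer time points in the by-visit DLQI display, and those removed have no valid denominator.
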